## Funding:

UHN Foundation and Princess Margaret Cancer Foundation

## Protocol Version Record

Version	Amendment	Date
1.0	Draft version for REB review	Oct 18th, 2024
1.1	Final version	April 1 st , 2025
1.2	Amendment	July 30 th , 2025

## **Background**

Primary brain tumors (PBTs), including gliomas (the most common PBT in adults), are a major public health burden worldwide. Global incidence rates are increasing and can reach up to 26 per 100,000 person-years. In Canada, 6,000 patients per year and 16 patients per day are diagnosed with PBTs. Although PBTs represent 2% of all malignancies, they are second only to stroke as a cause of mortality from neurologic diseases. Their functional consequences far outweigh their prevalence and subsequent high disability rates can severely strain healthcare systems.

With recent advancements in multimodal interventions (e.g., neurosurgery, radiotherapy, systemic therapy), patients with PBTs can survive longer.  However, early and delayed treatment complications may occur and range from mild transient side effects to disabling long-term sequelae, such as sensorimotor, cognitive, and psychosocial impairments as well as deconditioning, negatively impacting the quality of life of survivors.  Studies have shown that interprofessional rehabilitation can help address these issues and provide holistic and tailored care to both inpatients and outpatients. 

## Rationale

Even though rehabilitation is of paramount importance in patients with PBTs when compared to other malignancies due to their high risk of disability, it remains unclear when exactly rehab can be effectively and safely started due to a dearth of high-quality evidence and best practices. Nonetheless, rehabilitation should be initiated at some point to prevent complications, manage impairments, and maintain patients' functional independence regardless of life expectancy. The current brain cancer rehabilitation practice across Canada involves in-person service delivery in inpatient and outpatient settings after medical/surgical treatment and radiotherapy, respectively, if applicable. However, it is uncertain whether this practice represents the most effective model of care.

One of the goals of inpatient rehabilitation is to improve patients' functional abilities, facilitating their attendance and tolerance to radiation treatments, while outpatient rehabilitation is geared towards addressing the residual deficits arising from the cancer itself, the brain injury, as well as treatment complications. While cranial radiation is a proven curative and palliative intervention for PBTs,  it is not without toxicity, including cognitive and physical decline. There are various mechanisms by which radiation can induce brain injury, including reduction of neural precursors in the hippocampus, alteration of the cellular microenvironment, inflammation via oxidative damage, ischemia and neuronal excitotoxicity. Whether concurrent rehabilitation can be beneficial as both modes of treatment target the same organ requires further study. We know from stroke rehabilitation that rehabilitation provided hyperacutely within 24 hours of the injury to the brain is associated with poorer functional outcomes when

compared to usual care. A similar investigation on the timing of optimal rehabilitation in people with brain cancer is warranted.

While in-person rehabilitation remains the standard of care, the COVID-19 pandemic has accelerated the adoption of telerehabilitation, enhancing accessibility, participation, and patient experience for individuals with acquired brain injuries (ABI), and fostering improved clinical outcomes (e.g., to fatigue, depression, anxiety, insomnia, cognition, strength, balance and gait). To our knowledge, no studies on interprofessional, synchronous telerehabilitation have been conducted in adults with PBTs.

## **Overall Study Objectives**

We will conduct a pilot randomized controlled trial with an embedded qualitative component with the following objectives:

- To evaluate the feasibility, safety, and preliminary effectiveness of an interdisciplinary synchronous telerehabilitation program consisting of video-based individualized physiotherapy (PT), occupational therapy (OT), and/or speech language pathology (SLP) sessions, compared with current standard-of-care, on physical function, cognitive function, confidence to self-manage care, and quality of life for participants who are concurrently undergoing radiation therapy for glioma,
- To evaluate the feasibility of administering outcome measures of quality of life, recovery of impairment, fatigue and survival for a future definitive study
- 3. To understand the experiences of participants with telerehabilitation including the perceived impact on quality of life, as well as barriers and facilitators to participation

## **Hypotheses**

We hypothesize that:

 The telerehabilitation protocol will demonstrate sufficient feasibility (defined as ≥80% of participants completing the 8-week protocol) to support a larger, multisite randomized controlled trial.

## **Study Design**

The CoRR Study will use a two-arm pilot randomized controlled trial design to compare feasibility and preliminary effectiveness of active telerehabilitation (intervention) versus usual care (control), and involve quantitative and qualitative methods of data collection.

## Intervention groups

Active Rehab - outpatient rehabilitation delivered via synchronous, video-based telerehabilitation for 8 weeks; PTs, OTs and/or SLPs (depending on clinical need), twice per week for 50-minute sessions (for each discipline of clinical need) during Radiation Therapy (up to 8 weeks). Neurosurgeon or oncologist may also refer outpatient rehab through the Toronto Rehab

- ABI Day Hospital after Radiation Therapy if a participant meets the Toronto Rehab ABI Day Hospital acceptance criteria
- 2. Usual Care generic aerobic and strengthening exercise instructions and an 8-week subscription to BrainHQ during Radiation Therapy; Neurosurgeon or oncologist may also refer outpatient rehab through the Toronto Rehab ABI Day Hospital after Radiation Therapy if a participant meets the Toronto Rehab ABI Day Hospital acceptance criteria

#### Randomization

Participants will be stratified for glioma grade (grade <3, grade=4) and then randomly assigned to the 2 intervention groups using a 1:1 allocation ratio block design. The schedule will be randomly generated using the PLAN procedure (SAS 9.4, SAS Institute, USA).

## **Blinding**

Evaluators and the study statistician will be blinded to the group allocation, however, due to the nature of the intervention, participants and members of the research team cannot be blinded to group allocation.

## **Research Ethics**

Research Ethics approval will be obtained prior to starting the trial. The trial will be conducted in accordance with applicable regulations and guidelines on current Good Clinical Practice (GCP) guidelines.

## Participant Selection and Screening

The study aims to recruit up to 54 individuals who will undergo radiation therapy for intracranial gliomas from Princess Margaret Hospital Pencer Centre and Toronto Western Hospital neurosurgery service.

A member of the potential participants' circle of care (e.g., physical therapist, physician, social worker) will identify all patients who meet study inclusion and exclusion criteria:

### **Inclusion Criteria**

- 1. 18 year of age or older;
- 2. Planned to undergo an initial course of radiation for a diagnosis of intracranial glioma (any grade)
- 3. Recent brain surgery (within 12 weeks)
- 4. Eastern Cooperative Oncology Group (ECOG) performance status ≥ 1 at time of enrollment
- 5. Have a caregiver, friend, or family member available to provide physical support during the initial assessment session and Active Rehab sessions
- 6. Eligible to be prescribed Brain HQ and home exercise
- 7. Have an email address, or caregiver, friend or family member has an email address

- 8. Have cognitive-communicative ability to participate as per clinical judgement;
- Able to provide informed consent, or if not, availability of legal decision maker.
- 10. Access to a space with necessary therapy requirements (e.g. must have sturdy chair with armrests; if room is carpeted, must be low-pile, etc.);
- 11. Able to understand English to the point that they are able to follow instructions, and express levels of exertion, pain, distress, etc. as determined by the study team

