## **Baseline Evaluation**

At baseline, prior to the intervention beginning, the following data will be collected over video conferencing or as a self-administered questionnaire:

1. Participant Demographic Information Form

- 2. Participant Personal Information Form
- 3. Berg Balance Scale
- 4. Timed Up and Go Test
- 5. 30 Sec Sit to Stand Test
- The Arm Capacity and Movement Test (ArmCAM)
- 7. Brief Test of Adult Cognition by Telephone (BTACT)
- 8. Brief Visuospatial Memory Test Revised (BVMT)
- 9. Sustained Attention to Response Task (SART)
- 10. Wechsler Test of Adult Reading (WTAR)
- 11. Perceived Medical Condition Self-Management Scale
- 12. EuroQol-5 Dimension 5 Level (EQ-5D-5L)
- 13. Fatique Severity Scale

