#### 4-Week Evaluation

At the 4-week evaluation, we will collect the following data over video conferencing or as a self-administered questionnaire:

- 1. Berg Balance Scale
- 2. Timed Up and Go Test
- 3. 30 Sec Sit to Stand Test
- 4. The Arm Capacity and Movement Test (ArmCAM)
- 5. Brief Test of Adult Cognition by Telephone (BTACT)
- Brief Visuospatial Memory Test Revised (BVMT)
- 7. Sustained Attention to Response Task (SART)
- 8. Wechsler Test of Adult Reading (WTAR)
- Perceived Medical Condition Self-Management Scale
- 10. EuroQol-5 Dimension 5 Level (EQ-5D-5L)
- 11. Fatigue Severity Scale
- 12. Medical Information Update Form

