#### 8-Week Evaluation

At the 8-week evaluation, we will collect the following data over video conferencing or as a self-administered questionnaire:

- 1. Berg Balance Scale
- 2. Timed Up and Go Test
- 3. 30 Sec Sit to Stand Test
- 4. The Arm Capacity and Movement Test (ArmCAM)
- 5. Brief Test of Adult Cognition by Telephone (BTACT)
- 6. Brief Visuospatial Memory Test Revised (BVMT)
- 7. Sustained Attention to Response Task (SART)
- 8. Wechsler Test of Adult Reading (WTAR)
- 9. Perceived Medical Condition Self-Management Scale
- 10. EuroQol-5 Dimension 5 Level (EQ-5D-5L)
- 11. Fatigue Severity Scale
- 12. Medical Information Update Form

Any new medical diagnoses, adverse events, or changes in other medications will be noted.

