#### 26-Week Evaluation

At the 26-week evaluation, we will collect the following data over video conferencing or as a self-administered questionnaire:

- 1. Berg Balance Scale
- 2. Timed Up and Go Test
- 3. 30 Sec Sit to Stand Test
- 4. The Arm Capacity and Movement Test (ArmCAM)
- 5. Brief Test of Adult Cognition by Telephone (BTACT)
- 6. Brief Visuospatial Memory Test Revised (BVMT)
- 7. Sustained Attention to Response Task (SART)
- 8. Wechsler Test of Adult Reading (WTAR)
- 9. Perceived Medical Condition Self-Management Scale
- 10. EuroQol-5 Dimension 5 Level (EQ-5D-5L)
- 11. Fatigue Severity Scale
- 12. Medical Information Update Form
- 13. Semi-structured Interview about participant experiences with telerehab for those in the intervention group

Any new medical diagnoses, adverse events, or changes in medications will be noted.

The evaluators will be trained neuropsychologists/psychometrists, physiotherapists and occupational therapists. The participant's privacy during evaluations will be ensured by the use of pass codes to access the videoconference, personalized links or each participant to avoid unwanted participants, restricting screensharing to the evaluator, using the Lobby feature in Microsoft Teams, and the evaluators checking at the start of the evaluations if the participant is ok with their caregivers hearing the answers to questions asked.

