#### Risks related to telerehab:

Risk of falls, injury and cardiac events such as dysrhythmia, exertional angina, and muscular/joint strains. Telerehab groups will be supervised and emergency contact information will be provided by participants. Participants will obtain physician clearance for exercise and will have a caregiver present during telerehab sessions. All telerehab sessions provided as part of this study will be provided by specialized physiotherapists, occupational therapists and speech language pathologists with training in neuro-rehabilitation working in the Brain Rehab program, and they will be adhering to all Brain Rehab Program policies and procedures on safety during telerehab.

Principal Investigators will review and classify all adverse events as to severity, whether it was expected or not, and whether it was related to the intervention. Recruitment rate, dropouts at all stages, and reasons for non-completion will also be tracked.

Adverse events related to the telerehabilitation assignment or to other causes will be adjudicated by the PIs.

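### Physical support is required at the initial assessment and rehab sessions only, leaving the remote balance and mobility tests at weeks 4, 8, 12 and 26 without it in both arms

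*Protocol*

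**What the plan says.** Two places in the protocol deal with a person physically beside the participant.

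- Inclusion Criteria, item 5: "Have a caregiver, friend, or family member available to provide physical support during the initial assessment session and Active Rehab sessions". The term initial assessment session is not defined; the schedule calls the first visit the Baseline Evaluation.
- Risks related to telerehab: the section opens with "Risk of falls, injury and cardiac events such as dysrhythmia, exertional angina, and muscular/joint strains" and, among its controls, states that participants "will have a caregiver present during telerehab sessions". It does not mention the evaluations.

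The evaluations are remote throughout. At baseline "the following data will be collected over video conferencing or as a self-administered questionnaire"; the later sections use the same formula, for example "At the 4-week evaluation, we will collect the following data over video conferencing or as a self-administered questionnaire" and "At the 8-week evaluation, we will collect the following data over video conferencing or as a self-administered questionnaire". The week 12 and week 26 sections match. All five visits list the Berg Balance Scale, Timed Up and Go and 30-second sit to stand. Table 1 marks Berg and Timed Up and Go at all five visits; it lists a 3-metre walk test and omits the sit to stand.

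Caregivers or helpers appear at the evaluations in two other places. The 26-Week Evaluation section has evaluators check whether the participant minds caregivers hearing the answers. The text after Table 1 allows a helper, if the participant prefers, for completing self-report measures.

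**The concern.** The sponsor decided that someone must be available to give physical support at the initial assessment. The same performance tests, in the same remote mode, recur four more times without that condition, and no reason is given for the difference. Standing balance, rising from a chair and walking are tasks in which a fall can happen, and an evaluator on a screen cannot steady the participant. A site that follows the protocol to the letter can run every follow-up physical test with nobody in the room.

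What is at stake is chiefly participant safety and consistent conduct of the tests. There is also a small reporting consequence. The session-level safety measure under Secondary Outcomes counts adverse events in rehab sessions only. A fall during an evaluation would enter the percentage of patients with an adverse event but not the percentage of sessions with one.

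**Working it through.** No power, sample-size or error-rate figure is involved, and the protocol gives no figure of its own to reproduce. The check compares the texts and then counts sessions.

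**Step 1. Visits with physical performance tests, against the support condition**

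| Visit | Berg, Timed Up and Go, sit to stand listed | Mode | Physical support required |
|---|---|---|---|
| Baseline | Yes | Remote | Yes, if this is the initial assessment session |
| Week 4 | Yes | Remote | Not stated |
| Week 8 | Yes | Remote | Not stated |
| Week 12 | Yes | Remote | Not stated |
| Week 26 | Yes | Remote | Not stated |

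The visit sections offer video or a self-administered questionnaire. Observed performance tests cannot be done as a questionnaire, so they fall to video.

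**Step 2. Whether another provision fills the gap**

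- The check on whether caregivers may hear the answers concerns privacy. It allows that a caregiver may be nearby but does not require one.
- The helper mentioned after Table 1 is optional and is there for self-report measures.
- Inclusion criterion 10 concerns the room and furniture.
- Emergency contacts and physician clearance, in the risk section, concern response to an event and fitness to exercise.
- Evaluators are trained clinicians, but they are remote.

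None of these puts a person beside the participant.

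**Step 3. Count**

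Inputs: 54 participants, 27 per arm (Sample Size); 5 evaluations (visit sections and Table 1). Full follow-up is assumed, so the counts are upper bounds.

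- All evaluation sessions: 5 × 54 = 270.
- Outside the support condition: 4 × 54 = 216, and 216 / 270 = 80%.
- Per arm: 4 × 27 = 108, the same in telerehab and usual care.

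**Step 4. Sensitivity to the undefined term**

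If the initial assessment session means the intake assessment for rehabilitation and not the Baseline Evaluation, the baseline tests are uncovered too, and the count becomes 5 × 54 = 270 of 270. The figure of 216 uses the narrower gap.

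**The case against.** The strongest reply is that this is an omission, not a contradiction, and that practical safety steps for remote testing may sit in an assessor manual not shown here. Other controls exist: evaluators are trained neuropsychologists or psychometrists, physiotherapists and occupational therapists; the room must be suitable; emergency contacts are held; and participants need physician clearance for exercise. The privacy check suggests that caregivers will often be there anyway. The count measures sessions, not risk.

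Much of this stands. The protocol does not say that participants will be alone, and 216 is an upper bound on sessions without a stated requirement. It is not an estimate of falls. The objection does not remove the point, however. The protocol itself sets the support rule and fixes where it applies; a manual might add to that rule, but the protocol points to none.

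A reader might infer three stronger things that the documents do not support.

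- **That the gap biases the comparison between arms.** Criterion 5 binds every candidate before randomisation, so both arms enter with a person available for the initial assessment and for possible Active Rehab sessions. The missing requirement at follow-up is identical in both arms, and nothing in the protocol shows that tests would be skipped or altered more in one arm.
- **That a usual-care participant needs a helper at baseline only.** As an eligibility condition, criterion 5 asks more of every entrant than that, although usual-care participants then have no Active Rehab sessions to attend.
- **That the later tests are no safer than the first.** The Rationale cites cognitive and physical decline after cranial radiation as general background, but participants also enter within 12 weeks of brain surgery. The protocol does not rank risk by visit.

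**Conclusion.** The point holds as a gap in a stated safety condition and should be corrected. As written, the protocol requires physical support at no more than 1 of the 5 remote evaluations that include balance and mobility tests. That leaves 4 of 5 uncovered in both arms.

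The session count rests on three assumptions: 54 participants are enrolled, all are followed to week 26, and the initial assessment session is the Baseline Evaluation. Drop-out or death would lower the number of sessions; the other reading of the undefined term would raise it to all 270. The conclusion that support is not required at follow-up rests on the text alone and does not depend on these assumptions.

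The primary outcome (completion at week 8), the sample size and the planned analyses are unaffected, and the point is not evidence of bias in the physical outcomes.

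**What to change.** Reconcile inclusion criterion 5 and the section on telerehab risks with the five evaluation sections and Table 1.

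1. Define the initial assessment session and say whether it is the Baseline Evaluation.
2. Either extend the existing support condition to every remote evaluation that includes physical performance tests, in both arms, or state what equivalent safeguard the investigators apply at those visits. The choice of safeguard belongs to the sponsor and investigators.
3. While doing so, make the visit lists and Table 1 agree on which physical tests are given (30-second sit to stand or 3-metre walk), so that the condition attaches to a settled list.
4. Add one eCRF field recording whether a helper was present for the physical tests.

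The cost is a short amendment to the criterion and risk section, matching consent and assessor wording, and the eCRF field. Every entrant must already have such a person available, so the added burden is mainly a slightly longer commitment for helpers, to week 26. Some evaluations may need rescheduling. If physical tests are withheld when no helper is present, a few will be missed and will drop out of the complete-case analysis of secondary outcomes; the eCRF field would let the report separate those from other missing values.

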### **Exclusion Criteria**

- 1. Undergoing a repeat course of in-field repeat irradiation for a recurrent brain tumour;
- 2. Spinal glioma;
- 3. Currently receiving in-patient or outpatient rehabilitation;
- 4. Living in long-term care;
- 5. Severe vision or hearing loss, impacting ability to participate actively in rehab:
- 6. Planned surgery that would preclude or affect participation in the protocol
- 7. Contraindications to radiation therapy (e.g. pregnancy, or trying to conceive)

Inclusion and exclusion criteria will be assessed by reviewing the patient's medical and social history including review of the following screening data:

[figure not shown]
- 1. Glioma grade
- 2. Prior occurrence(s) of tumour
- 3. Presence of severe hearing/vision loss
- 4. Current participation in neuro-rehabilitation
- 5. Place of residence

The member of circle of care will inform potential participants about the study opportunity and share the recruitment materials containing the contact information of the research team. Once a patient has indicated their interest to a circle of care member, the circle of care member will pass on their contact information via phone or secure internal UHN email to the study coordinator, who will then approach the patient in person or via a phone call to explain the study, and ask if they would like to receive the consent form to review. If the patient prefers using e-mail for research-related communication, study coordinator will

obtain the patient's permission to use e-mail and will note it in the study files. The study coordinator will share a copy of the consent form via their preferred method (e.g. posted in the mail, e-mail or in person) with those who express interest and allow adequate time to read the consent form and discuss it with family and/or care providers. If the patient decides to proceed with the study, research coordinator will schedule a session to answer any questions and obtain consent. Participants will also be recruited through self-referral using study flyers posted in the designated areas at UHN.

